### 6.1.6 Study Documentation

The Investigator will acknowledge that he/she has received a copy of the Afrezza IB and assures the Sponsor that he/she will comply with the protocol. No changes in this protocol can be made without the Sponsor's written approval.

## 6.2 Data Management and Quality Control

### 6.2.1 Case Report Forms

The Investigator should maintain adequate and accurate source documents and trial records that include all pertinent observations on each of the site's trial subjects. Source data should be attributable, legible, contemporaneous, original, accurate, and complete.

All clinical data will be captured in a validated database or CRF.

The Investigator site staff will enter and edit the data via a secure network, with secure access features (username and password) and/or on a paper CRF. A complete audit trail will be maintained. The Investigator will approve the data using an electronic and/or physical signature, and this approval will be used to confirm the accuracy of the data recorded. CRFs will be used for all subjects. The subject data will be accessible from the Investigator's site throughout the trial. The CRF must be kept current to reflect subject status at each phase during the course of the trial. The CRF will not capture personalized data. The Investigator must make a separate confidential record of personalized details (name and initials) on the subject identification and enrollment log.

It is the responsibility of the Investigator of the respective site to ensure that all subject discontinuations or changes in study or other medications entered in the subject's CRF are also made on the subject's medical records. The CRFs for any subject leaving the study should be completed at the time of the final visit or shortly thereafter.

### 6.3 Study Monitoring and Quality Assurance

This study will be performed in compliance with the Sponsor's standard operating procedures (SOPs) or with the contract research organization's SOPs, if applicable, and with regulations set forth by the FDA, ICH, and other significant regulatory authorities. Compliance will be achieved through study-specific audits of clinical sites and review of data. The Investigator or their qualified designee will enter the information required by the protocol on CRFs provided by the

Confidential Page 66 of 70

Sponsor. Site monitors should visit each clinical site at a frequency documented in the monitoring plan to review CRFs for completeness and accuracy. Any discrepancies found between source documents and completed CRFs should be queried and appropriate clinical site personnel should address and or correct those discrepancies.

Computerized and manual procedures should be used to review and check data from CRFs and data from external sources for omissions, apparent errors, and values that may require further clarification from the clinical site. Data queries will be addressed by appropriate clinical personnel in the CRF. Only authorized personnel can make corrections to CRF in the clinical database and all corrections are documented in the CRF audit trail.

#### 6.4 Retention of Records

The Investigator must arrange for retention of study records at the site. The Investigator should take measures to prevent accidental or premature destruction of these documents for the duration of the retention period.

The Investigator and institution must agree to provide direct access to all study-related materials, study staff, facilities, and source documents for study monitors, auditors, or regulatory inspectors.

# 6.5 Use of Study Findings

By signing the study protocol, the Investigator agrees to the use of results of the study for the purposes of national and international registration. If necessary, the authorities will be notified of the Investigator's name, address, qualifications, and extent of involvement. Reports covering clinical and biometric aspects of the study will be prepared by the Sponsor or its representative.

#### 6.6 Financial Disclosure

The Investigator will be required to disclose any financial equity interests in the Sponsor and any conflicts of interest.

### 6.7 Publications and Disclosure Policy

This clinical study will be registered on ClinicalTrials.gov no later than 21 days after the first subject is enrolled, in compliance with applicable regulatory requirements.

As a multicenter trial, the Sponsor intends to publish clinical data from all centers participating in the investigation. Authorship and manuscript composition will reflect joint cooperation between multiple Investigators, sites, and the Sponsor's personnel. Authorship will be established before writing of the manuscript.

In conformity with International Committee of Medical Journal Editors (ICMJE 2019) recommendations, Investigators whose contribution consists solely in the collection of data will not be named individually as authors. Rather, those Investigators may be included in a collective

Confidential Page 67 of 70

mannkind

authorship (e.g., "Clinical Investigators") or acknowledged individually with their contribution(s) specified.

Individual Investigators and/or their associates subsequently may publish additional findings of this study in scientific journals or present them at scientific meetings, provided that the Sponsor is given ample opportunity to review and authorize the disclosure of data for any proposed abstract, manuscript, or slide presentation before its submission. This review is required to ensure that the Sponsor authorizes the presentation of the data prior to disclosure.

Confidential Page 68 of 70

Protocol Title: ABC [Afrezza with Basal Combination]: A Phase 4 Study of Mealtime Control with Afrezza in Adult Subjects with Type 1 Diabetes Mellitus in Combination with an Automated Insulin Pump or Insulin Degludec

Brief Title: Afrezza With Basal Combination (ABC)

Protocol Number: MKC-TI-192

Clinical Phase: Phase 4

SAP Document Version: Version 1.0

SAP Note: Redacted sections describe Data Management procedures for the study. Only Statistical sections are presented.

Sponsor: MannKind Corporation, [name]

NCT Number: NCT05243628

Data Management & Statistical Analysis Plan

Protocol Title	ABC [Afrezza with Basal Combination]: A Phase 4 Study of Mealtime Control with AfreZZA in Adult Subjects with Type 1 Diabetes Mellitus in Combination with an Automated Insulin Pump or Insulin Degludec
Protocol Identifier	MKC-TI-192
Protocol Version	1.1
Sponsor/Local Sponsor	MannKind Corporation
Document Version	1.0

1. Version History

Version	Summary of Change(s)	Author
1.0	Initial Version	[name] & [name]

2. Purpose

The purpose of this Statistical Analysis Plan (SAP) is to detail procedures and methods for executing the evaluation of primary and secondary endpoints. The study is not powered for statistical analysis.

3. Scope

This DMP & SAP cover study-related tasks and deliverables for the above referenced study. It describes how data will be collected, processed, QC'ed, stored, and analyzed.

4. Definitions & Acronyms

The following table lists the study terms specific-to and only used in this document

Term	Definition
A1c / HbA1c	Hemoglobin HbA1c

AE	Adverse Event
AID	Automatic Insulin Delivery
CGM	Continuous Glucose Monitor/Monitoring
CRF	Case Report Form
CSR	Clinical Study Report
DM	Data Manager
DMP	Data Management Plan
RAA	Rapid-acting insulin analogue
SAE	Serious Adverse Event
SAP	Statistical Analysis Plan
SMBG	Self-monitoring of blood glucose
(e)TMF	(electronic) Trial Master File

[figure not shown]
5. Data Storage

Database	Database Owner	Description of Data Stored
[REDACTED]	[REDACTED]	[REDACTED]
[REDACTED]		[REDACTED]
[REDACTED]		[REDACTED]
[REDACTED]	[REDACTED]	[REDACTED]

6. Data Collection and Processing

[REDACTED]	[REDACTED]

6.1 Data Locks

7. Randomization

7.1 Randomization List Generation

The DM will create a master randomization list; however, no formal validation will be performed. Subject assignments will be predetermined and distributed ahead of time to ensure enrollment stratification and criteria are met. Microsoft Excel's "rand" function will be used to generate and assign a study arm group for each subject in the study in advanced with the following criteria:

1. A total of 25 subjects
2. Three study arms:
 - a. Afrezza + AID (total of 10 subjects)
 - b. Afrezza + Degludec (total of 10 subjects)
 - c. AID Control (total of 5 subjects)
3. Study arms 1 and 3 must have a minimum of 3 subjects each from AID systems at screening:
 - a. Medtronic 670G/770G
 - b. Tandem Control IQ
4. Site 001 will have 12 subjects
5. Site 002 will have 13 subjects
6. The total number of subjects in each study arm will be approximately split evenly between sites.

Throughout enrollment, the data manager may rearrange randomization assignments manually if criterion 3 is not being met.

The sites will not have visibility to which study arm they will be assigned ahead of subject randomization.

If a subject drops after randomization and the site intends to enroll another subject to meet their total enrollment goal (criteria 4 and 5), the study arm assignment for that subject will be moved to the bottom of the list or wherever appropriate to ensure the criteria are met.

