7.2 Randomization Assignment

As subjects are randomized into the study, the subject ID, AID system at screening, and status (active enrollment or dropped) will be tracked on the master randomization list.

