8.3 General Considerations

All statistical processing will be performed using the most current version of statistical software (such as MiniTab, MATLAB, or Microsoft Excel) at the time of the analysis.

Summary tables (descriptive statistics and/or frequency tables) will be provided for screening and/or baseline variables, efficacy variables, and safety variables.

Continuous variables will be described by descriptive statistics (n, mean, median, standard deviation, minimum, and maximum). Frequency counts and percentage of subjects within each category will be provided for categorical data. Individual data will be listed and sorted by treatment, subject ID, visit, and time point. Database lock will occur upon the completion of the study.

Signatures for

I am the Author of this document:

Name: **[name]**
[name]

As the Author I approve this document

2022-03-30 19:35:41 (UTC-07:00)

Electronically Signed in

Timestamp

Content Approval:

I approve this Content

Name: **[name]**
[name]

2022-03-30 19:40:40 (UTC-07:00)

Electronically Signed in

Timestamp

Content Approval:

I approve this Content

Name: **[name]**
[name]

2022-03-30 20:39:27 (UTC-07:00)

Electronically Signed in

Timestamp

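### The allocation list is an unvalidated Excel draw that doubles as the live tracker and may be reordered by hand, and the readable SAP states no seed, archived original or change log

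*SAP*

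**What the plan says.** SAP 7.1 (Randomization List Generation) sets out how the list is made. On checking, it says: "The DM will create a master randomization list; however, no formal validation will be performed". The generator is Excel's RAND, which "function will be used to generate and assign a study arm group for each subject in the study in advanced with the following criteria". Six criteria follow:

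- 25 subjects in total (criterion 1)
- arms of 10, 10 and 5 (criterion 2)
- a minimum number of users of each AID system in study arms 1 and 3 (criterion 3)
- 12 subjects at site 001 and 13 at site 002 (criteria 4 and 5)
- an approximately even split of each arm between the sites (criterion 6)

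The list is fixed before enrolment: "Subject assignments will be predetermined and distributed ahead of time to ensure enrollment stratification and criteria are met". It can still change afterwards. During enrolment "the data manager may rearrange randomization assignments manually if criterion 3 is not being met", and when a randomized subject drops out and the site intends to enrol another, that assignment "will be moved to the bottom of the list or wherever appropriate to ensure the criteria are met".

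SAP 7.2 (Randomization Assignment) makes the list the working record as well: subject ID, AID system and "status (active enrollment or dropped) will be tracked on the master randomization list". Under SAP 7.3 the site e-mails the sponsor at Visit 2 with the subject ID and AID system, and the sponsor replies with the arm.

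Protocol 5.5 gives the ratio as 2:2:1. It sets AID-system minimums of 3 + 3 in each Afrezza arm and 2 + 2 in AID Control.

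**The concern.** An allocation list can be trusted after the fact if it can be regenerated (a seed and a program), if it was frozen (a dated copy taken before the first subject), or if every change to it was logged. The readable SAP states none of these. It waives formal validation outright, so this is a stated procedure and not just a missing detail.

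The source of the allocation and the sheet edited through enrolment are the same document, and the SAP permits two kinds of edit by judgement. If the list at database lock differs from the list drawn, nothing in the readable plan would show whether the cause was a permitted move, a slip, or the draw itself.

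What is at stake is the ability to show that the arms of a small open-label study were formed at random. No error rate is involved, because the plan makes no test.

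**Working it through.** **1. The plan's totals.** Arms: 10 + 10 + 5 = 25 (SAP 7.1). Sites: 12 + 13 = 25 (SAP 7.1). The 2:2:1 ratio of Protocol 5.5 applied to 25 gives 25 × 2/5 = 10, 25 × 2/5 = 10 and 25 × 1/5 = 5. The totals agree.

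**2. Can the list be recovered from the plan?** The number of orderings with these totals is 25! / (10! × 10! × 5!) = 9,816,086,280. The site constraints reduce this but leave a very large number. Without a seed or a saved copy, the list drawn cannot be identified. As a demonstration, a script with a fixed seed returned the same 25-row list on a second run, and two runs without a fixed seed gave different lists.

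**3. How likely are manual edits?** Criterion 3 triggers rearrangement.

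- *As written.* It asks for 3 users of each of two systems in study arms 1 and 3. The arms are lettered a to c. If arm 3 is item c (AID Control), it needs 3 + 3 = 6 subjects in an arm of 5. It can never be met, so the permission to rearrange is always open.
- *With the minimums of Protocol 5.5 instead.* Let M of the 25 subjects use one system, and let a, b and c be their numbers in the three arms. For a list not stratified by system, the chance of meeting all minimums is the sum of C(10,a) × C(10,b) × C(5,c) / C(25,M) over a + b + c = M, with a and b from 3 to 7 and c from 2 to 3. For M = 12 this is 3,367,440 / 5,200,300 = 0.65.

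| Users of one system, of 25 (assumed) | Minimums met by chance | Not met |
|---|---|---|
| 12 or 13 | 0.65 | 0.35 |
| 10 or 15 | 0.47 | 0.53 |
| 8 or 17 | 0.13 | 0.87 |

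The documents do not give the mix of systems, so the rows show a range. Even with a near-even mix, about one list in three would need a change.

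**4. Size of one error.** One misassigned subject is 1/5 = 20% of AID Control or 1/10 = 10% of an Afrezza arm. A wrong arm count would show in a tally of 25 rows. Two rows exchanged between arms would leave every total intact and would not show.

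**The case against.** Several stronger readings are tempting, and the documents do not support them.

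- *The allocation cannot be checked.* The list is predetermined, so a copy saved before the first subject would allow a check. The SAP 7.3 e-mails also record the arm issued to each subject outside the workbook. This stands, with one limit: the e-mails show which arm was issued, not that it was the arm drawn.
- *Nobody checks the list.* The SAP waives formal validation only. It says assignments are set in advance so that the criteria are met, and it has the data manager act on criterion 3. An informal check may well take place.
- *No archived copy exists.* The data storage and the data collection and processing sections are redacted and may describe one. Only the readable text can be judged.
- *Typing into the tracker redraws the list.* That needs live formulas to be kept in the arm column, which the SAP does not say. If RAND is only a sort key for 25 labelled rows, the arm labels do not change.
- *RAND would almost never give the required totals.* If each arm were drawn independently at 0.4, 0.4 and 0.2, the chance of exactly 10, 10 and 5 would be 9,816,086,280 × 0.4^20 × 0.2^5 = 3.5%. With 5/5/2 at site 001 and 5/5/3 at site 002 it would be 0.4%. If approximately even is taken to allow 4 to 6 per site in each Afrezza arm and 2 or 3 controls per site, it is 1.7%. With fixed totals, sorting labelled rows is the more natural method and always meets the arm totals. These figures are therefore not evidence against the plan.
- *The lack of a seed creates selection bias.* Sites cannot see upcoming arms, and eligibility is confirmed before the arm is requested. Those protections hold whatever the generator.

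The study is also descriptive. The SAP says it is not powered, Protocol 5.6 expects no statistical significance, and the primary objective is change within each group. That limits the consequence but does not remove the point, because the protocol still presents the study as randomized with a control arm.

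**Conclusion.** The point holds as a weakness in traceability. An Excel list whose formal validation is waived also serves as the live tracker and may be reordered by hand. With no seed, archived original or change log in the readable SAP, it is not assured that an error or a later edit could be distinguished from the random draw. Manual edits are likely: certain to be permitted if criterion 3 means 3 + 3 in AID Control, and needed with probability about 0.35 to 0.87 under the Protocol 5.5 minimums for the assumed mixes of AID system.

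The consequence is for the credibility of the allocation. It does not by itself bias the HbA1c or CGM summaries, and no test is affected. The conclusion rests on the readable SAP and would narrow if the redacted sections provide for a frozen copy and version control. It is a cheap improvement worth making, not a flaw that invalidates the design.

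**What to change.** 1. **SAP 7.1, generation and check.** Replace the RAND sentence and the waiver of validation with: the list is a random permutation of the fixed arm totals within each site, generated by a script with a recorded seed; before the first assignment, a second sponsor staff member re-runs the script and checks the list against criteria 1, 2, 4, 5 and 6; the list is archived as a dated read-only file. SAP 8.3 already gives MiniTab and MATLAB as examples of analysis software, and either could run the script, although that section concerns analysis and not list generation.
2. **SAP 7.2, tracking.** Keep tracking in a separate file that records the list row used for each subject. Log every reassignment or slot move with its date and reason. The log is needed because 7.1 still allows both kinds of move after the list is frozen.
3. **Criterion 3.** Reconcile it with Protocol 5.5 (3 + 3 in each Afrezza arm, 2 + 2 in AID Control). Protocol 3.1 words the minimum differently again, as at least 5 users of each system, and should be aligned at the same time. Monitor this criterion during enrolment: under SAP 7.3 the sponsor learns a subject's AID system only with the Visit 2 request, so it cannot be checked in advance.

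The cost is about an hour of existing staff time (an estimate), plus a log line per change. Arms, sites and sample size stay as they are.

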7.2 Randomization Assignment

As subjects are randomized into the study, the subject ID, AID system at screening, and status (active enrollment or dropped) will be tracked on the master randomization list.

7.3 Study Site Randomization Procedures

After clinical sites confirm subject eligibility at Visit 2, they will e-mail the Sponsor at [contact], requesting randomization assignment with:

- The subject ID
- The subject's AID system at screening

The Sponsor must reply as soon as possible with the assigned study arm from the master randomization list, such that the site may continue the visit.

8. Statistical Analysis

8.1 Study Objectives

The primary objective of this study is to evaluate the change in HbA1c from baseline to end of study in adults ≥ 18 years of age with T1DM for each of the three following groups:

- AfreZZa + AID: AfreZZa for bolus (mealtime) in combination with use of a CSII pump with an AID algorithm using a RAA for basal and correction insulin coverage
- AfreZZa + Insulin Degludec: AfreZZa for bolus (mealtime and correction) in combination with insulin degludec for basal insulin coverage
- AID Control: CSII pump with an AID algorithm using an RAA for all bolus (mealtime and correction) and basal insulin coverage

The secondary objectives of this study are to:

Evaluate the safety of study treatment based on hypoglycemia event rate, based on SMBG (self-monitored blood glucose testing), and severe hypoglycemia incidence rate in adults ≥ 18 years of age with T1DM for each of the three following groups:

- AfreZZa + AID
- AfreZZa + Insulin Degludec
- AID Control

Evaluate the impact of study treatment on overall glycemic control when comparing baseline versus end of treatment period as measured by core CGM metrics based on G6 Pro data:

- Change in percent time in range (TIR), defined as time spent with glucose in the range of 70 to 180 mg/dL
- Change in percent time below range (TBR), defined as time spent with glucose < 70 mg/dL
- Change in percent time spent with glucose < 54 mg/dL

- Change in percent time above range (TAR), defined as time spent with glucose >180 mg/dL
- Change in percent time spent with glucose >250 mg/dL
- Change in glycemic variability as measured by coefficient of variation (CV)

The above metrics to be evaluated on each of the three following groups in adults ≥ 18 years of age with T1DM for each of the three following groups:

- Afrezza + AID
- Afrezza + Insulin Degludec
- AID Control

8.2 Statistical Methods

8.2.1 Sample Size Determination

The sample size (25 subjects completing the study) was not determined using statistical methods.

8.2.2 Analysis Populations

All randomized subjects in the clinical study will be included in the Intent-To-Treat (ITT) Population. ITT subjects who have no major protocol deviations that would have an impact on the primary endpoint assessment will be included in the Per-Protocol (PP) Population.

In general, any data for endpoint analysis collected outside the allowed study visit window may be considered missing for the PP population. Participants with early termination will be included in ITT analyses, as applicable, based on the amount of data collected relevant to the analysis. A summary of data exclusion and rationale will be included in the CSR.

8.2.3 Descriptive Summary of Efficacy

HbA1c values will be summarized at baseline and end of study. CGM values and metrics will be summarized by visit. A summary table with descriptive statistics (n, mean, median, standard deviation, minimum, and maximum) will be provided. CGM data will also be presented graphically.

8.2.4 Descriptive Summary of Safety

The incidence (number of events) of hypoglycemia confirmed by SMBG (total and severe) and the percentage time (by CGM) with glucose below 70 mg/dL and below 54 mg/dL will be reported. Nocturnal is defined as midnight to 0600 and severe hypoglycemia is defined as an event requiring assistance of another person to actively administer carbohydrate, glucagon, or other resuscitative actions. The number and percentage of subjects with treatment-emergent AEs will be tabulated by system, organ class, and preferred term by relationship to treatment, and by severity.

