#### 2.2 Secondary Objectives

The secondary objectives of this study are:

- To evaluate the safety of study treatment based on hypoglycemia event rate and severe hypoglycemia incidence rate in adults ≥18 years of age with T1DM for each of the three following groups:
  - o Afrezza + AID
  - Afrezza + Insulin Degludec
  - AID Control
- To evaluate the impact of study treatment on overall glycemic control when comparing baseline versus end of treatment period as measured by core CGM metrics:
  - Change in percent time in range (TIR), defined as time spent with glucose in the range of 70 to 180 mg/dL
  - Change in percent time below range (TBR), defined as time spent with glucose
     mg/dL
  - Change in percent time spent with glucose <54 mg/dL

  - Change in percent time above range (TAR), defined as time spent with glucose
     180 mg/dL
  - Change in percent time spent with glucose >250 mg/dL
  - o Change in glycemic variability as measured by coefficient of variation (CV)
- The above metrics to be evaluated on each of the three following groups in adults ≥18 years of age with T1DM for each of the three following groups:
  - o Afrezza + AID
  - o Afrezza + Insulin Degludec
  - AID Control

Confidential Page 21 of 70

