### 3.9.2.6 Hypoglycemic Events

A hypoglycemic episode is defined as any event with SMBG <70 mg/dL (i.e., Level 1 hypoglycemia) or SMBG <54 mg/dL (i.e., Level 2 hypoglycemia) (ADA 2021a) on the study-provided glucose meter. Severe hypoglycemic events are defined as events requiring assistance of another person to actively administer carbohydrate, glucagon, or other resuscitative actions. Severe hypoglycemic events will be documented as SAEs in the CRF. Nonsevere hypoglycemic events will not be documented as AEs but will be recorded in the hypoglycemia page of the CRF.

After the standardized meal challenge at Visit 2, subjects will be monitored for signs of hypoglycemia. Subjects exhibiting signs of hypoglycemia will be treated as appropriate (e.g., provided with a snack or glucose). The type of treatment given and time will be recorded and subjects will remain in-clinic until hypoglycemia is resolved.

In the event that the subject accidentally enters carb intake/meal announcement for a certain meal and also doses with Afrezza, carbohydrates or glucagon should be administered. The subject should be instructed to contact the Investigator and site staff as soon as possible following the event to ensure prompt review and to give the Investigator the opportunity to address any further necessary measures for correction.

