### 5.4.1 Safety Endpoints

- Event rates and incidence Level 1 (<70 mg/dL) and Level 2 (<54 mg/dL) hypoglycemic events as confirmed by SMBG
- Event rates and incidence of severe hypoglycemic events, defined as events requiring assistance of another person to actively administer carbohydrate, glucagon, or other resuscitative actions
- Incidence and severity of AEs: TEAEs, SAEs, AESIs, and device complaints
- Change in FEV1 from screening to end of study

Confidential Page 62 of 70

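### SAP 8.2.4 summarises SMBG hypoglycemia as a count of events, total and severe only, and so does not deliver the event rates and by-level incidence set as objective and endpoint

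*SAP*

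**What the plan says.** SAP 8.1 sets the safety objective, for each of the three groups, as "hypoglycemia event rate, based on SMBG (self-monitored blood glucose testing), and severe hypoglycemia incidence rate". Protocol 2.2 has the same pair: "hypoglycemia event rate and severe hypoglycemia incidence rate". Protocol 5.4.1 makes the endpoint more specific: "Event rates and incidence Level 1 (<70 mg/dL) and Level 2 (<54 mg/dL) hypoglycemic events as confirmed by SMBG". A second bullet there asks for event rates and incidence of severe events.

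SAP 8.2.4 is the only SAP section that says how hypoglycemia will be summarised. It commits to "The incidence (number of events) of hypoglycemia confirmed by SMBG (total and severe", and adds the percentage of CGM time below 70 and below 54 mg/dL. The same section tabulates treatment-emergent AEs by number and percentage of subjects.

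Three other statements bear on the point. SAP 8.3 gives a general rule: "Frequency counts and percentage of subjects within each category will be provided for categorical data". Protocol 3.9.2.6 separates the two kinds of event: severe ones are entered as SAEs, whereas "Nonsevere hypoglycemic events will not be documented as AEs but will be recorded in the hypoglycemia page of the CRF". The SAP's opening note says of the blacked-out parts: "Redacted sections describe Data Management procedures for the study. Only Statistical sections are presented".

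**The concern.** The SAP sets a rate as its objective and then specifies a count. A number of events has no denominator, so it is not a rate, and it does not say how many subjects were affected, so it is not an incidence proportion either. The total category also merges Level 1 and Level 2. The only figure at 54 mg/dL in 8.2.4 is CGM time, which is a different measure from SMBG-confirmed events.

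Allocation is 2:2:1, so a table of raw counts invites a misleading comparison between each Afrezza arm and control. Descriptive tables are all that this study will produce, and hypoglycemia is the first secondary objective. The choice of summary measure therefore matters even though nothing is tested.

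**Working it through.** **Which required measures have a planned summary**

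| Measure | Required by | Planned summary |
|---|---|---|
| SMBG <70 mg/dL, event rate | SAP 8.1, protocol 5.4.1 | None; 8.2.4 gives a count |
| SMBG <70 mg/dL, subjects affected | Protocol 5.4.1 | None named |
| SMBG <54 mg/dL, event rate | Protocol 5.4.1 | None |
| SMBG <54 mg/dL, subjects affected | Protocol 5.4.1 | None named |
| Severe, event rate | Protocol 5.4.1 | None; 8.2.4 gives a count |
| Severe, subjects affected | SAP 8.1 (incidence rate read as a proportion of subjects), protocol 5.4.1 | Treatment-emergent AE table, because severe events are SAEs |

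Protocol 5.15 and the synopsis safety summary also promise incidence without a rate and without SMBG levels, so part of the gap is inherited. Neither equates incidence with a number of events; that gloss appears only in the SAP.

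**Size of the effect of using counts**

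Inputs from the documents: arms of 10, 10 and 5 (SAP 7.1), which sum to 25 in the ratio 2:2:1; 90 days from V2 to V14 (protocol 3.1); replacement of subjects who leave within 4 weeks but not later (protocol 3.3.1.3.2); all randomized subjects kept in ITT (SAP 8.2.2). The plan states no event rate, so there is no figure of its own to reproduce.

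Assumptions: the same event rate in every arm, 90 days per completer, and a dropout's observed time and events are counted.

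1. Expected count = rate × subject-days. Each Afrezza arm has 10 × 90 = 900 and control has 5 × 90 = 450. The count ratio is 900/450 = 2.0 at any common rate. Conversely, 20 events in each of an Afrezza arm and control would be 20/(900/365.25) = 8.1 versus 20/(450/365.25) = 16.2 per patient-year.

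2. One control subject leaves at day 30 and is not replaced: 4 × 90 + 30 = 390 subject-days. Count ratio 900/390 = 2.31. Per head, (900/10)/(390/5) = 90/78 = 1.15.

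3. One Afrezza subject leaves at day 30 instead: 9 × 90 + 30 = 840. Count ratio 840/450 = 1.87. Per head, (840/10)/(450/5) = 84/90 = 0.93.

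4. One Afrezza subject leaves at day 28, is replaced and stays in ITT: 900 + 28 = 928 subject-days over 11 subjects, or 84.4 days each. Per head against control, 84.4/90 = 0.94.

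The true rate ratio is 1.00 in cases 1 to 4, apart from the 20-versus-20 illustration in case 1.

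5. Count against proportion, as an illustration: 6 events in a 10-subject arm can be 1/10 (10%) of subjects if one has them all, or 6/10 (60%) if six have one each. The summary line shows 6 either way.

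**The case against.** The best defence is that little is lost. The SAP says plainly that "The study is not powered for statistical analysis". Events are recorded at every visit and individual data will be listed by treatment and subject (SAP 8.3), so with 25 subjects a reader could see whether events cluster and could compute rates. Dividing by the known arm sizes removes the 2:1 artefact. The residual is small against noise. At assumed rates of 10 and 60 events per patient-year, expected counts over 90 days are 24.6 versus 12.3 and 147.8 versus 73.9. The approximate Poisson 95% range for a true ratio of 1 is exp(±1.96 × √(1/a + 1/b)), where a and b are the two expected counts. That is 0.50 to 1.98 at the lower rate and 0.76 to 1.32 at the higher, before any overdispersion. A distortion of 7% to 15% sits inside both. The dropout at day 30 is also close to the earliest exit that goes unreplaced; later exits shrink the effect. All of this stands, and it limits the severity. Listings do not replace the summary measure that the objective names, however.

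SAP 8.3 might be said to supply percentages of subjects. It does not name hypoglycemia, gives no rate, and does not override the explicit gloss in 8.2.4. Redaction does not help either, since the SAP describes the hidden parts as data management.

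Three stronger readings are tempting and should not be drawn:

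- A reader might infer that severe incidence is missing too. Severe events are entered as SAEs (protocol 3.9.2.6) and nonsevere ones are not AEs, so the hypoglycemia row of the treatment-emergent AE table should show the number and percentage of subjects with severe events. Only the severe event rate is absent.
- A reader might infer that screening-period events will inflate the counts, because recording starts at V1. The documents set no explicit counting window, but no text says that screening events will be pooled, and the objective concerns safety of study treatment.
- A reader might infer that the SAP departs from its governing protocol. The SAP cites protocol version 1.1 and the protocol supplied is 2.0. The revision history lists no change to these endpoints, and the conflict between SAP 8.1 and 8.2.4 stands whichever version applies.

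**Conclusion.** The point holds as a mismatch between the stated objective and endpoint and the planned summary. SAP 8.2.4 does not provide the SMBG event rate, the event rates and subject proportions for Level 1 and Level 2, or the severe event rate. Severe subject incidence should already be covered.

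Raw counts at equal risk would read 2:1 for each Afrezza arm against control. After division by arm size, a single early exit leaves 1.15 or 0.93 in the examples. Those figures rest on a common event rate, 90 days per completer and one assumed dropout at day 30 whose observed data are counted.

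No test, power statement or primary result is affected. The data are collected and listed, so the endpoint is not lost. This is a minor but real correction to a stated rule that gives the wrong measure.

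**What to change.** In SAP 8.2.4, replace the count gloss with four quantities per arm: number of events; subject-time from randomization to V14 or early termination; events per subject-time; and n (%) of subjects with at least one event. Give them for SMBG <70 mg/dL, SMBG <54 mg/dL and severe events, using the existing definition of severe.

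Two counting rules must be settled before lock, because a rate cannot be reproduced without them:

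- State whether the <70 category includes readings <54. Protocol 3.9.2.6 gives Level 1 no lower bound.
- State how repeat low readings are counted. Footnote f to protocol Table 3 treats every meter reading below 70 as an episode, while section 3.9.2.6, to which it refers, speaks of events; the two need reconciling.

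Align protocol 5.15 and the synopsis safety summary with 5.4.1, so that the protocol's own summary section matches its endpoints.

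The cost is a short wording change and minor programming. No new data are needed: hypoglycemic events are recorded at every visit (protocol Table 3), and study meter downloads are scheduled at V2, V9, V13 and V14 (protocol Table 4).
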